## 9.1. DISCONTINUATION OF STUDY TREATMENT

### 9.1.1. Liver Chemistry Stopping Criteria

Discontinuation of study treatment for abnormal liver function should be considered by the Investigator when a participant meets one of the conditions outlined in [Figure 2](#) or if the Investigator believes that it is in best interest of the participant.

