## 9. DISCONTINUATION OF STUDY TREATMENT AND PARTICIPANT DISCONTINUATION/WITHDRAWAL

It may be necessary for a participant to permanently discontinue study treatment (nirogacestat) early. In this case, the participant will return to the site for an EOT visit and a post dose safety

follow-up (FUP) visit (refer to SoA; [Section 1.3](#) for a complete list of required assessments to be conducted).

Reasons for discontinuation of study treatment at any time may include:

- Clinical (including physical examination) or radiographic (using RECIST v1.1) evidence of progressive disease (PD);
  - Treatment after Initial Evidence of Disease Progression
    - Study treatment may be continued at the investigator's discretion if the participant is clinically stable as defined by the following criteria:
      - Absence of clinical signs and symptoms of disease progression
      - No decline in ECOG performance status
      - Absence of progressive tumor at critical anatomical sites (e.g., cord compression) requiring urgent alternative medical intervention.
    - The participant will be reassessed at the next protocol-defined CT or MRI scan for tumor measurement in order to rule out pseudo-progression.
      - If repeat imaging demonstrates CR, PR, or SD compared to the first scan that showed disease progression, treatment with study treatment may be continued.
      - If repeat imaging demonstrates PD, defined as  $\geq 10\%$  increase in tumor burden compared to the first scan that showed disease progression, participants should be discontinued from study treatment.
    - All decisions to continue study treatment beyond initial progression must be discussed with the Medical Monitors and documented in source documents.
  - Adverse events requiring removal from protocol therapy as stated in [Section 9.1](#). Any SAE (refer to [Appendix A5-1.3](#) for SAE criteria), clinically significant AE (refer to QTcF stopping criteria, [Section 9.1.2](#)), severe laboratory abnormality (refer to liver chemistry stopping criteria, [Section 9.1.1](#)), any grade  $\geq 3$  hypersensitivity reaction, anaphylaxis, intercurrent illness, or other medical condition which indicates to the Investigator that continued participation is not in the best interest of the participant;
  - The initiation of emergent treatment (e.g., radiotherapy, surgery, or systemic therapy including chemotherapy, small molecule inhibitors, immunotherapy, or targeted therapy) for granulosa cell tumor;

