Details of liver chemistry stopping criteria and required actions and follow-up assessments after liver stopping or monitoring event are given in [Section 9.1.1](#) and [Appendix A4-3](#).

Only required at Screening to establish eligibility and/or Baseline and permit full investigation of clinical observations on study. eGFR is calculated using the Chronic Kidney Disease Epidemiology Collaboration (CKD-EPI) equation. See [Appendix A4-5](#).

Microscopy examination is performed only if blood or protein is abnormal.

Serology only required at Screening

Participants reporting Adverse Events (AEs)/Adverse Events of Special Interest (AESIs)/Serious Adverse Events (SAEs) of reproductive system disorders will have hormone levels assessed every 3 months until event resolution (or for at least 90 days after discontinuing study treatment).

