## A4-3. LIVER SAFETY: SUGGESTED ACTIONS AND FOLLOW-UP ASSESSMENTS

Liver Chemistry Stopping Criteria	
ALT-absolute	ALT $\geq$ 5 $\times$ ULN
ALT Increase	ALT $\geq$ 3 $\times$ ULN persists for $\geq$ 4 weeks
Bilirubin	ALT $\geq$ 3 $\times$ ULN and total bilirubin $\geq$ 2 $\times$ ULN ( $>$ 35% direct bilirubin)
INR^2	ALT $\geq$ 3 $\times$ ULN and International normalized ratio (INR) $>$ 1.5, if INR measured
Cannot Monitor	ALT $\geq$ 3 $\times$ ULN and cannot be monitored weekly for 4 weeks
Symptomatic	ALT $\geq$ 3 $\times$ ULN associated with symptoms (new or worsening) believed to be related to liver injury or hypersensitivity
Suggested Actions, Follow-up Assessments, and Monitoring	
Actions	

 
Immediately discontinue study treatment (nirogacestat)
 
Report the event to the Sponsor within 24 hours
 
Complete the liver event in the electronic Case Report Form (eCRF) and complete the SAE eCRF form if the event also met the criteria for an SAE
 
Perform liver chemistry follow-up assessments
 
Monitor the participant until liver chemistry test abnormalities resolve, stabilize, or return to baseline (see MONITORING)
 
Restart/rechallenge is not allowed per protocol and not granted, permanently discontinue study treatment and continue participant in the study for any protocol specified follow up assessments
 
	

Follow-Up Assessments	

• Viral hepatitis serology

• Obtain INR and recheck with each liver chemistry assessment until the transaminase values show downward trend

• Serum CPK and LDH

• Fractionate bilirubin, if total bilirubin <math>\geq 2 \times \text{ULN}</math>

• Obtain complete blood count with differential to assess eosinophilia

• Record the appearance or worsening of clinical symptoms of liver injury, or hypersensitivity, on the AE eCRF page

• Record use of concomitant medications (including acetaminophen, herbal remedies, and other over-the-counter medications) on the concomitant medications eCRF page

• Record alcohol use in the eCRF if AE is related to alcohol use

	

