
If <math>\text{ALT} \geq 3 \times \text{ULN}</math> AND <math>\text{bilirubin} \geq 2 \times \text{ULN}</math> or <math>\text{INR} > 1.5</math>:
 

• Anti-nuclear antibody, anti-smooth muscle antibody, Type 1 anti-liver kidney microsomal antibodies, and quantitative total Immunoglobulin G (IgG) or gamma globulins

• Serum acetaminophen adduct High performance liquid chromatography (HPLC) assay (quantifies potential acetaminophen contribution to liver injury in participants with definite or likely acetaminophen use in the preceding week (James, 2009)).

• Liver imaging (ultrasound, magnetic resonance, or computerized tomography) and/or liver biopsy to evaluate liver disease; complete liver

• Notify the medical monitor within 24 hours of learning of the abnormality to discuss participant safety

• Participant can continue study treatment

• Participant must return weekly for repeat liver chemistry tests (ALT, AST, alkaline phosphatase, bilirubin) until the abnormalities resolve, stabilize or return to baseline

• If at any time, the participant meets liver chemistry stopping criteria, proceed as described in Section 9.1.1

	

If, after 4 weeks of monitoring, <math>\text{ALT} < 3 \times \text{ULN}</math> and <math>\text{bilirubin} < 2 \times \text{ULN}</math>, monitor participants twice monthly until liver chemistry tests resolve, stabilize, or return to baseline
	
Monitoring	

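### Section 9.1.1 leaves stopping for liver criteria to the investigator's judgement, while Appendix A4-3 orders immediate, permanent discontinuation under a heading that calls it suggested

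*Protocol*

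**What the plan says.** Section 9.1.1 of the protocol consists of one lead sentence and Figure 2. The sentence says that discontinuation "should be considered by the Investigator when a participant meets one of the conditions outlined in" Figure 2, and adds as an alternative trigger the investigator's view of the participant's best interest.

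Appendix A4-3 lists the liver stopping criteria and then the actions, under the heading "Suggested Actions, Follow-up Assessments, and Monitoring". The actions are orders: stop study treatment at once; restart or rechallenge is "not allowed per protocol and not granted"; and the site is told to "permanently discontinue study treatment and continue participant in the study for any protocol specified follow up assessments". The event must be reported to the sponsor within 24 hours. A separate block for increased monitoring states "Participant can continue study treatment".

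Three other places bear on the question:

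- Section 9 lists, among the reasons for stopping, "Adverse events requiring removal from protocol therapy as stated in" Section 9.1 and points to 9.1.1 for liver chemistry. The list is introduced by "Reasons for discontinuation of study treatment at any time may include", and the item ends in a clause on the investigator's judgement.
- Table 14, footnote 2, points to both Section 9.1.1 and Appendix A4-3: "Details of liver chemistry stopping criteria and required actions and follow-up assessments after liver stopping or monitoring event are given in" these two places.
- Table 7 sends hepatic toxicities to Section 9.1.1.

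**The concern.** Two safety instructions for the same event differ in force. One asks the investigator to think about stopping; the other tells the investigator to stop and never restart. The second is weakened by its own heading. A site that works from the lead sentence of 9.1.1 could keep dosing a participant who has met a stopping criterion, including a possible Hy's Law case, and believe that it was following the protocol. The 24-hour report would alert the sponsor, but only after the site had made its decision, and the trial has no Data Monitoring Committee. Elevated liver transaminases are a named identified risk of nirogacestat in Section 4.3, so the situation is foreseeable.

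What is at stake is the safety of participants still on treatment. Neither the objective response rate nor any SAP analysis depends on it: SAP Section 5.6.4 tabulates participants who meet the criteria whether or not dosing stopped.

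**Working it through.** No statistical formula applies, so the check is a comparison of texts.

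**Step 1. Scope of the conflict.** A4-3 lists these stopping criteria:

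1. ALT ≥ 5 × ULN
2. ALT ≥ 3 × ULN for at least 4 weeks
3. ALT ≥ 3 × ULN with total bilirubin ≥ 2 × ULN (more than 35% direct)
4. ALT ≥ 3 × ULN with INR > 1.5
5. ALT ≥ 3 × ULN when weekly monitoring for 4 weeks is not possible
6. ALT ≥ 3 × ULN with symptoms of liver injury or hypersensitivity

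That makes 6 criteria, all based on ALT. Footnote 2 of A4-3 flags numbers 3 and 4 as possible Hy's Law, so 2 of 6.

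**Step 2. Force of each text on stopping.**

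| Place | Force |
|---|---|
| Section 9.1.1, lead sentence | Discretionary |
| Section 9, reasons for discontinuation | Mixed: speaks of required removal, but in an optional list that ends in investigator judgement |
| Table 14, footnote 2 | Directive: calls the actions required |
| A4-3, actions | Directive in content, suggested in heading |
| A4-3, footnote 1 | Directive: stop even when bilirubin cannot be fractionated |

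The count is 1 discretionary, 1 mixed and 3 directive. The balance suggests that mandatory stopping was intended.

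**Step 3. Does any cross-reference settle precedence?**

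- Table 14, footnote 2, names 9.1.1 and A4-3 together and ranks neither.
- Table 7 points to 9.1.1 only.
- The monitoring text of A4-3 sends a participant who later meets a stopping criterion back to 9.1.1.
- The line under Figure 2 makes A4-3 compulsory reading, but only for participants who are to be monitored weekly.

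None of these gives A4-3 precedence. Two of the four lead to the discretionary sentence.

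**Step 4. Comparison with the neighbouring rules.** In Section 9.1.2, a participant whose QTcF criterion is confirmed on triplicate ECGs will be withdrawn from treatment. In Section 9.1.3, a participant who becomes pregnant will be withdrawn. Of the three stopping rules in Section 9.1, only the liver rule is worded as a matter to consider.

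**Step 5. Can one act satisfy one text and breach the other?** Yes. An investigator who considers stopping and continues dosing has done what the 9.1.1 sentence asks and has broken the A4-3 order.

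**The case against.** The strongest reply is that the operative rule may sit in Figure 2, whose body could not be read. Its title covers both stopping and increased monitoring. A sentence introducing both branches could not order everyone to stop, since A4-3 lets the monitoring group continue. On that reading the 9.1.1 wording is an umbrella and the stopping branch may already be firm. This stands as a limit on the size of the defect. It does not remove it: the introductory sentence would then be softer than the figure it introduces, and the suggested label would remain.

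A second reply is that A4-3 is the specific text and its words are plain, that Table 14 calls the actions required, and that Section 11 bars waivers. A site that follows A4-3 complies with everything. This shows what the sponsor probably meant, but a site acting on 9.1.1 would not think that it needed a waiver.

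A third reply is that harm is conjectural: a site would have to overlook A4-3, and the event is reportable within 24 hours. It is true that no frequency can be given. Entry criteria (AST and ALT at most 2 × ULN, no known liver disease) also lower the chance of an event without removing it.

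Two smaller points are fair. The QTcF rule says withdrawn but does not say permanently, so it is a model for firmness and not for every detail. The A4-3 table is broken in the extracted text, so the place where it permits continued dosing has to be read with care; the conflict itself does not depend on row order.

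**Conclusion.** The concern holds. The lead sentence of Section 9.1.1 and the actions in Appendix A4-3 differ in force for the same event, and no text that could be read resolves the difference. The conflict reaches all 6 liver stopping criteria, 2 of them possible Hy's Law. No number of affected participants is offered, because the documents give no rate of liver stopping events, no count of participants still on treatment and no basis for how often a site would keep dosing.

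The conclusion assumes that the conditions in Figure 2 correspond to the A4-3 criteria and that the figure carries no statement of precedence. If its stopping branch is directive, the defect is confined to the lead sentence and the suggested labels. Confidence is medium for that reason. The change should be made, as a matter of participant safety.

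**What to change.** In Section 9.1.1, state that study treatment will be stopped immediately and permanently, without rechallenge, once any A4-3 stopping criterion is met. Keep investigator discretion for other liver abnormalities and for the weekly-monitoring group (ALT ≥ 3 and < 5 × ULN, bilirubin < 2 × ULN, no symptoms, able to be monitored weekly for 4 weeks). Remove *suggested* from the A4-3 stopping actions, from the appendix title and from the matching label under Figure 2. Confirm that Figure 2 agrees; if its stopping branch is already firm, only the lead sentence and the labels need to change.

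The cost is one sentence, the label edits and a check of the figure. A clarification letter could reach sites before the amendment. Nothing is given up except latitude that A4-3 already denies, and the SAP needs no change.

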**Figure 2: Liver Chemistry Stopping Criteria and Increased Monitoring Algorithm**

➤ If participant is to be monitored weekly, must refer to Liver Safety: Suggested Actions and Follow-up Assessments ([Appendix A4-3](#))

### 9.1.2. QTcF Stopping Criteria

If a clinically significant finding is identified (including, but not limited to changes from baseline in QT interval corrected using Fridericia's formula [QTcF]), the Investigator or qualified designee will determine if the participant can continue in the study and if any change in participant management is needed. This review of the ECG printed at the time of collection must be documented. Any new clinically relevant finding should be reported as an AE.

A participant who meets either of the following bulleted criterion should be confirmed with triplicate ECGs. If these findings are confirmed based on the average of the triplicate readings, the participant will be withdrawn from the study treatment:

- QTcF > 500 msec
- Change from baseline of QTcF > 60 msec

[Table 8](#) describes the discontinuation criteria for participants with underlying bundle branch block.

**Table 8: Bundle Branch Block Discontinuation Criteria**

Baseline QTcF with Bundle Branch Block	Discontinuation QTcF Threshold with Bundle Branch Block
< 450 msec	> 500 msec
450 to 480 msec	≥ 530 msec

QTcF = QT interval corrected using Fridericia's formula; msec = millisecond

See the SoA ([Section 1.3](#)) for data to be collected at the time of treatment discontinuation and follow-up and for any further evaluations that need to be completed.

### 9.1.3. Pregnancy

A participant who becomes pregnant will be withdrawn from study treatment. See [Section 11.3.6](#) for additional details.

## 9.2. PARTICIPANT DISCONTINUATION/WITHDRAWAL FROM THE STUDY

A participant may withdraw from the study at any time at his/her own request or may be withdrawn at any time at the discretion of the Investigator for safety, behavioral, compliance, or administrative reasons. This is expected to be uncommon.

At the time of discontinuing from the study, if possible, the EOT visit should be conducted. See SoA ([Section 1.3](#)) for specific data to be collected at the time of study discontinuation, as well as follow-up for any further evaluations that need to be completed.

If the participant withdraws consent for disclosure of future information, the Sponsor may retain and continue to use any data collected before such a withdrawal of consent.

If a participant withdraws from the study, they may request destruction of any samples taken and not tested. The Sponsor must be notified if the participant requests destruction of sample, and the Investigator must document this in the site study records.

### **9.3. LOST TO FOLLOW UP**

A participant will be considered lost to follow-up if they repeatedly fail to return for scheduled visits and is unable to be contacted by the study site.

The following actions must be taken if a participant fails to return to the clinic for a required study visit:

- The site must attempt to contact the participant and reschedule the missed visit as soon as possible and counsel the participant on the importance of maintaining the assigned visit schedule and ascertain whether the participant wishes to and/or should continue in the study.
- Before a participant is deemed lost to follow up, the Investigator or designee must make every effort to regain contact with the participant (where possible, 3 telephone calls and, if necessary, a certified letter to the participant's last known mailing address or local equivalent methods). These contact attempts should be documented in the participant's medical record.
- Should the participant continue to be unreachable, they will be considered to have withdrawn from the study.

Discontinuation of specific sites or of the study as whole is handled as part of [Appendix A1-7](#).

### **10. DURATION OF STUDY**

The study will continue until at least the date that the survival data needed for the estimate of 2-year overall survival is obtained, or the study is prematurely stopped due to futility.

### **11. STUDY ASSESSMENTS AND PROCEDURES**

- Study procedures and their timing are summarized in the SoA ([Section 1.3](#)).
- Protocol waivers or exemptions are not allowed.
- Immediate safety concerns should be discussed with the Sponsor immediately upon occurrence or awareness to determine if the participant should continue or discontinue study treatment.
- Adherence to the study design requirements, including those specified in the SoA is essential and required for study conduct.
- All screening evaluations must be completed using a Pre-Enrollment Review Form, which should be provided to the Medical Monitor at least two days prior to C1D1 for review to confirm that potential participants meet all eligibility criteria ([Section 7.1](#) and

[Section 7.2](#)). The electronic data capture (EDC) will capture all participants who sign the ICF, including all screen-failures.

- The amount of blood collected from each participant will be approximately 350 mL each year during the study. This does not include any extra assessments that may be required for unscheduled assessments or EOT/FUP visits. Repeat or unscheduled samples may be taken for safety reasons or for technical issues with the samples.
- In the event that a study site or participant is unable to complete a study visit or procedure due to restrictions caused by a public health emergency such as COVID-19, the following accommodations may be allowed temporarily with prior approval from the Medical Monitor. Any deviations from the study protocol due to a public health emergency should be documented in the source data and electronic Case Report Form (eCRF) and reported to the IRB/IEC in accordance with their reporting requirements.
  - If a study participant cannot attend a study visit onsite due to a public health emergency, they may be able to attend a local hospital/clinic or arrange for a telehealth or home healthcare visit.
  - Clinical laboratory assessments (safety labs and pregnancy tests) may be performed locally with results and local laboratory normal values entered into the eCRF.
  - Electrocardiograms may be performed locally. If ECGs are performed locally, ECG tracings should be collected, and the Investigator (or designee) assessment should be documented.
  - Study imaging should be performed per the schedule in the SoA ([Section 1.3](#)); however, imaging may be performed at another imaging center (locally to the participant) with prior Medical Monitor approval.

## 11.1. EFFICACY ASSESSMENTS

### 11.1.1. Tumor Imaging

Tumor response will be assessed by CT or MRI (contrast required unless contraindicated). The same imaging modality and radiographic procedure used to assess disease sites at Screening is required to be used throughout the study (i.e., the same contrast protocol for scans). Tumor response and progression of cancer under study in real time will be evaluated locally at each study site according to RECIST v1.1 ([Eisenhauer 2009](#)). See [Appendix 3](#) RECIST Criteria response definitions. All RECIST measurements will be done by the site's local radiologist.

Chest imaging using CXR or CT (contrast not required) will also be required as described in the SoA and should be obtained per institutional standards.

Standard of care scan(s) acquired prior to the participant signing ICF may be used as the participant's screening visit scans if they were obtained within 28 days of the first dose of study treatment.

On treatment scans may be acquired (-) 7 days prior to the study visit or within the study visit window as described in the SoA ([Section 1.3](#)).

Imaging must be done prior to tumor biopsy if assessments occur on the same day.

Whenever disease progression is suspected (e.g., symptomatic deterioration) throughout the study, unscheduled scans may be acquired.

### **11.1.2. Other Objective Parameters**

#### **11.1.2.1. Patient-Reported Outcomes (PROs)**

Patient-reported Outcomes (PROs) will be assessed at each clinic visit using the Functional Assessment of Cancer therapy Ovarian Cancer Symptom Index (FOSI). The FOSI is an 8-question evaluation scored on a Likert scale of 0-4 from not at all to very much. Metrics assessed include lack of energy, vomiting, pain, nausea, swelling in stomach area, concern condition will get worse, quality of life assessment and stomach cramps. When possible, the participant should complete the paper FOSI questionnaire as the first assessment during the applicable study visits (refer to the SoA; [Section 1.3](#)) to minimize bias. This assessment takes approximately 5 minutes to complete and is manually calculated to determine a symptom index score correlating with level of patient symptoms ([Beaumont et al. 2007](#)). Change from baseline in the FOSI score and individual responses will be scored at each applicable study visit, EOT, and the safety FUP.

